9.0 STUDY PLAN

9.1 Study Procedures

The following sections describe the study procedures and data to be collected. For each procedure, subjects are to be assessed by the same investigator or site personnel whenever possible. The Schedule of Study Procedures is located in [Appendix A](#).

9.1.1 Informed Consent Procedure

The requirements of the informed consent are described in Section [15.2](#).

Informed consent must be obtained prior to the subject entering into the study, and before any protocol-directed procedures are performed, including requesting that a subject fast for laboratory evaluations.

A unique subject identification number (subject number) will be assigned to each subject at the time that informed consent is obtained; this subject number will be used throughout the study.

9.1.2 Demographics, Medical History, and Medication History Procedure

Demographic information to be obtained will include date of birth, sex, race as described by the subject, height, weight, caffeine consumption, xanthine consumption, alcohol use, reproductive status (including last menstrual period) and smoking status of the subject at Screening.

Medical history to be obtained will include determining whether the subject has any significant conditions that resolved at or prior to signing of informed consent. Ongoing conditions are considered concurrent medical conditions (see Section [9.1.7](#)).

Medication history information to be obtained includes any medication relevant to eligibility criteria stopped at or within 28 days prior to signing of informed consent.

9.1.3 Physical Examination Procedure

A baseline physical examination (defined as the assessment prior to first dose of study drug) will consist of the following body systems: (1) eyes; (2) ears, nose, throat; (3) cardiovascular system; (4) respiratory system; (5) gastrointestinal system; (6) dermatologic system; (7) extremities; (8) musculoskeletal system; (9) nervous system; (10) lymph nodes; and (11) other.

Any abnormal finding on a predose physical examination assessment must be assessed as not clinically significant (NCS) or clinically significant (CS) by the investigator and recorded in the source document and eCRF. All CS findings/changes will be recorded as a predose event or concurrent medical condition in the source document and on the appropriate eCRF described in Section [10.0](#) or Section [9.1.7](#). Any abnormal findings at Screening or prior to first dose, will exclude the subject from participating.

On subsequent examinations, any abnormal change or new diagnosis as a result of the abnormal change, compared to physical examination prior to first dose, as determined by the investigator, will be recorded as an AE in source documentation and on the AE eCRF described in Section [10.0](#).

9.1.4 Weight, Height and BMI

A subject should have weight and height measured while wearing indoor clothing and with shoes off. The BMI is calculated using metric units with the formula provided below. Height is recorded in centimeters without decimal places. Weight is collected in kilograms (kg) with 1 decimal place. BMI should be derived as:

$$\text{Metric: BMI} = \text{weight (kg)/height (m)}^2$$

Note that although height is reported in centimeters, the formula uses meters for height; meters can be determined from centimeters by dividing by 100. Thus, for example, if height=176 cm (1.76 meters) and weight=79.2 kg, then $\text{BMI}=79.2/1.76^2=25.56818 \text{ kg/m}^2$.

The values should be reported to 1 decimal place by rounding. Thus, in the above example BMI would be reported as 25.6 kg/m^2 . If the BMI is used as an entry criterion based on the 18.5 to 30.0 kg/m^2 cut-off point, then this determination must be made after rounding.

9.1.5 Vital Sign Procedure

Vital signs will include body temperature oral measurement, respiratory rate, sitting blood pressure (resting at least 5 minutes), and pulse (bpm).

When vital signs are scheduled at the same time as blood draws, the blood draw will take priority and vital signs will be obtained within 0.5 hour before or after the scheduled blood draw.

9.1.6 Documentation of Concomitant Medications

Concomitant medication is any drug given in addition to the study medication. These may be prescribed by a physician or obtained by the subject over the counter. Concomitant medication is not provided by Takeda. At each study visit, subjects will be asked whether they have taken any medication other than the study medication (used from signing of informed consent through the end of the study), and all medication including vitamin supplements, over-the-counter medications, and oral herbal preparations, must be recorded in the eCRF. Administration of any concomitant medications will result in exclusion of the subject from the trial. Documentation will include generic medication name, dose, unit, frequency, route of administration, start and end dates, and reason for use.

9.1.7 Documentation of Concurrent Medical Conditions

Any abnormal medical conditions, abnormalities in laboratory, ECG or physical examination findings found at Screening will exclude the subject from participating in this clinical trial.

9.1.8 Procedures for Clinical Laboratory Samples

All samples will be collected in accordance with acceptable laboratory procedures. Laboratory samples will be taken following a minimum 8-hour overnight fast on the days stipulated in the Schedule of Study Procedures ([Appendix A](#)).

[Table 9.a](#) lists the tests that will be obtained for each laboratory specimen.

Table 9.a Clinical Laboratory Tests

Hematology	Serum Chemistry	Urinalysis
RBC	ALT	pH
WBC with differential (Neutrophils, Eosinophils, basophils, Lymphocytes, Monocytes)	Albumin Alkaline phosphatase AST Total bilirubin	Specific gravity Protein Glucose Blood
Hemoglobin	Direct bilirubin (a)	Ketones
Hematocrit	Total protein	Urine color
Platelets	Creatinine	Presence of bile pigments
ESR	Blood urea nitrogen Creatine kinase γ -Glutamyl transferase Potassium Sodium Glucose	Microscopic Analysis: RBC/high power field WBC/high power field Epithelial cells, casts, etc
Diagnostic Screening:		
Serum		Urine (b)
HIV test, syphilis test		Drug screen including amphetamines, barbiturates, benzodiazepines, cannabinoids, cocaine, opiates and cotinine.
Hepatitis panel, including HBsAg and anti-HCV		
Female Subjects only:		Female Subjects only:
FSH (c)		hCG (for pregnancy) for female subjects of child bearing potential

ALT=alanine aminotransferase, AST= aspartate aminotransferase, ESR=erythrocyte sedimentation rate, FSH=follicle-stimulating hormone, hCG=human chorionic gonadotropin, RBC=red blood cell, WBC=white blood cell.

(a) Direct bilirubin will be measured only if total bilirubin is elevated.

(b) Urine screen for the presence of drugs of abuse will also be conducted on Day-1 and Days 3 and 4 of each study period (alcohol will be measured by administering an alcohol breath test at these time-points).

(c) At Screening, if menopause is suspected (defined as at least 12 months since last regular menses) and subject is not surgically sterile. FSH must be >40 IU/L to confirm menopausal status.

The local laboratory will perform laboratory tests for hematology, serum chemistries, and urinalysis. The results of laboratory tests will be returned to the investigator, who is responsible for reviewing and filing these results.

If subjects experience ALT or AST >3 ×upper limit of normal (ULN), follow-up laboratory tests (at a minimum, serum alkaline phosphatase, ALT, AST, total bilirubin, GGT, and international normalized ratio [INR]) should be performed within a maximum of 7 days and preferably within 48 to 72 hours after the abnormality was noted. (Refer to Section 10.2.3 for the appropriate guidance on reporting abnormal liver function tests.)

If the ALT or AST remains elevated >3 ×ULN on these 2 consecutive occasions, the investigator must contact the Medical Monitor for consideration of additional testing, close monitoring, possible discontinuation of study drug, discussion of the relevant subject details and possible

alternative etiologies. The abnormality should be recorded as an AE (please refer to Section 10.2.3 for reporting requirements).

The investigator will maintain a copy of the laboratory accreditation and the reference ranges for the laboratory used.

Laboratory reports must be signed and dated by the investigator indicating that the report has been reviewed and any abnormalities have been assessed for clinical significance.

All laboratory abnormalities must be recorded as an AE in the subject's source documents and on the appropriate eCRF. A clinically significant laboratory abnormality that has been verified by retesting will be followed until the abnormality returns to an acceptable level or a satisfactory explanation has been obtained.

9.1.9 Contraception and Pregnancy Avoidance Procedure

From signing of informed consent, throughout the duration of the study, and for 35 days after last dose of study medication, female subjects of childbearing potential* who are sexually active with a nonsterilized male partner** must use an effective or highly effective method of contraception from the list below.

In addition, they must be advised not to donate ova during this period.

The following definitions apply for contraception and pregnancy avoidance procedures.

* A woman is considered a woman of childbearing potential, ie, fertile, following menarche and until becoming postmenopausal unless permanently sterile. Permanent sterilization methods include hysterectomy, and bilateral oophorectomy. A postmenopausal state is defined as no menses for 12 months without an alternative medical cause. A high follicle stimulating hormone (FSH) level in the postmenopausal range (FSH >40 IU/L) may be used to confirm a postmenopausal state in younger women (eg, those <45 years old) or women who are not using hormonal contraception or hormonal replacement therapy. However, in the absence of 12 months of amenorrhea, a single FSH measurement is insufficient.

** Sterilized males should be at least 1 year post-bilateral vasectomy and have confirmed that they have obtained documentation of the absence of sperm in the ejaculate or have had bilateral orchidectomy.

Highly effective methods of contraception are defined as those, alone or in combination, that result in a low failure rate (ie, less than a 1% failure rate per year when used consistently and correctly). In this study, where medications and devices containing hormones are excluded, highly effective methods of contraception are:

Non-Hormonal Methods

- Copper T PLUS condom or spermicide.
- Bilateral Tubal Occlusion.

- Vasectomized partner (provided that partner is the sole sexual partner of the trial participant and that the vasectomized partner has received medical assessment of the surgical success.

Genotoxicity/teratogenicity/embryotoxicity is unlikely to be caused by the investigational drugs. Therefore, an effective method of contraception where there may be a higher than 1% failure rate can be used. An effective method of contraception is:

Barrier methods:

- Double-barrier method (contraceptive sponge, diaphragm or cervical cap with spermicidal jellies or creams PLUS male condom).

Female subjects must discontinue any use of hormonal contraceptives (if applicable), at least 2 months before the start (Day-1) of the trial.

Subjects will be provided with information on effective and highly effective methods of contraception as part of the subject informed consent process and will be asked to sign a consent form stating that they understand the requirements for avoidance of pregnancy and donation of ova during the course of the study.

During the course of the study, regular urine human chorionic gonadotropin (hCG) pregnancy tests will be performed only for women of childbearing potential and subjects will receive continued guidance with respect to the avoidance of pregnancy as part of the study procedures ([Appendix A](#)). In addition to a negative urine hCG pregnancy test at Screening, subjects also must have a negative urine hCG pregnancy test at Check-in (Day-1 of each Period) prior to receiving any dose of study medication.

9.1.10 Pregnancy

If any subject is found to be pregnant during the study, she should be withdrawn and any sponsor-supplied drug should be immediately discontinued. In addition, any pregnancies in the partner of a male subject during the study or for 35 days after the last dose should also be recorded following authorization from the subject's partner.

If the pregnancy occurs during administration of active study medication, or within 35 days of the last dose of active study medication, the pregnancy should be reported immediately, using a pregnancy notification form, to the contact listed in [Section 1.0](#).

If the subject and/or female partner of a male subject agree to the primary care physician being informed, the investigator should notify the primary care physician that the subject or female partner of the subject was participating in a clinical study at the time she became pregnant and provide details of the dose that the subject received.

All reported pregnancies will be followed up to final outcome, using the pregnancy form. The outcome, including any premature termination, must be reported to the sponsor. An evaluation after the birth of the child will also be conducted.

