(a) Screening may consist of 1 or more visits. Subjects will sign an informed consent form at the first visit and return to the clinic in a fasted state for safety laboratory testing at the second visit.

(b) Subjects are admitted into the clinic on Day -1 of each period (~Day 7 of the preceding period for Periods 2, 3, and 4).

(c) Randomization occurs on Day 1 of Period 1. Subjects check out of the unit on Day 2 following the 24-hour blood sample collection but return to the clinic for the 36-hour blood sample collection on Day 2 and on Days 3 and 4 of each period to complete study procedures.

(d) Follow-up call will be made 14 days ±2 days following the last dose of study drug.

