9.3.4 Final Visit/ Early Termination

If a subject discontinues, the reason for discontinuation must be documented in the source document and eCRF. The PK sample collection should be collected at the Early Termination Visit, if possible and relatively close to a protocol-specified time point. The site may seek guidance. For example, collect samples if early withdrawal is due to an AE, and/or if several hours elapsed since last blood draw.

Final Visit procedures will be performed on Day 4 of Period 4.

For all subjects receiving study drug, the investigator must complete the End of Study eCRF page.

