9.3.5 Follow-Up Visit/Telephone Call

At 14 days \pm 2 days following the last dose of study drug a Follow-up telephone call will be made by the site to inquire for any ongoing AEs or SAEs, new AEs or SAEs, and concomitant medications taken since final dose of study medication. Subject who withdrew consent should still be contacted for a safety Follow-up telephone call, but the contact should only be recorded in the medical records and not in the eCRF, according to data protection regulations.

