Appendix A Schedule of Study Procedures

Study Day:	Days -28 to -2 (b)	Drug Intake Periods 1 through 4 (a)					Study Exit (Day 4 of Period 4)/ Early Termination Visit	Follow-up Phone Call (d)
		Day -1 (Check-in)	Day 1 (c)	Day 2	Day 3	Day 4 (Periods 1, 2, and 3)		
Informed consent	X							
Inclusion/exclusion criteria	X	X						
Demographics and medical history	X							
Medication history	X							
Physical examination	X	X					X	
Vital signs (e)	X	X	X			X	X	
Height, weight and BMI	X							
Concomitant medications	X	X	X	X	X	X	X	X
12-lead ECG (f)	X	X					X	
Clinical laboratory evaluations (g)	X		X (h)				X	
Urine drug, cotinine, and alcohol breath screen	X	X			X	X	X	
Urine pregnancy test (hCG) (i)	X	X					X	
HBsAg, Anti-HCV, HIV, and syphilis (i)	X							
Confinement		X	X (j)	X (j)				
Study drug dosing (k)			X					
PK blood collection (l)			X	X	X	X	X	
Predose/AE assessment (m)	X	X	X	X	X	X	X	X

Footnotes are on the following page.

CONFIDENTIAL

- (a) There will be at least 7 days between the dose in 1 period and the dose in a subsequent period.
- (b) Screening may consist of 1 or more visits. Subjects will sign an informed consent form at the first visit and return to the clinic in a fasted state for safety laboratory testing at the second visit. Screening procedures must be performed within 28 days prior to administration of investigational product.
- (c) Day 1 of each drug intake period.
- (d) Follow-up phone call will be made 14 ± 2 days after study exit to inquire about any AE or SAEs, and concomitant medications taken since final dose. Any AE/SAE spontaneously reported within 30 days postdose will be included within the database as AEs.
- (e) Vital signs: oral body temperature, sitting blood pressure (after resting 5 minutes), respiratory rate, and pulse (beats per minute). Vital signs will be measured just prior to dosing on Day 1 of periods 1 through 4. When vital signs are scheduled at the same time as blood draws, the blood draw will take priority and vital signs will be obtained within 0.5 hour before or after the scheduled blood draw.
- (f) ECG performed at Screening, Check-in (Day -1 of Period 1), and Study Exit Day 4 of Period 4, or if a subject terminates early from the study.
- (g) Hematology, serum chemistries, and urinalysis tests will be done at a local laboratory.
- (h) Predose hematology, serum chemistries, and urinalysis tests will be done for Period 1 only.

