- (i) A urine pregnancy test and HBsAg, Anti-HCV, HIV, and syphilis tests will be done locally.
- (j) Following the 24-hour blood sample collection on Day 2 of each period, subjects will be discharged from the clinic and will return to the clinic for the 36-hour blood sample collection on Day 2 and on Days 3 and 4 of each period to complete study procedures.
- (k) Study drug will be administered on Day 1 of each period at 08:00 (± 1) hours, following an 8- hour fast. Dosing may be staggered to help facilitate logistics at the site.
- (l) Blood samples for PK obtained predose (within 15 minutes prior to dose), 0.25, 0.5, 1, 1.5, 2, 3, 4, 6, 8, 12, 16, 24, 36, 48, and 72 hours postdose. The PK sample should not be collected at the Early Termination Visit if a PK collection is not scheduled.
- (m) Predose AEs will be captured immediately following the signing of the informed consent at Screening until dosing on Day 1 of Period 1. The routine collection of AEs will continue through to the follow-up phone call.

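### Section 9.1.10 says pregnancies up to 35 days after the last dose should be reported or recorded, but nothing scheduled after Study Exit, 3 days after that dose, tests for or asks about them

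*Protocol*

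**What the plan says.** Protocol Section 9.1.10 deals with two groups. For subjects, if a pregnancy occurs during administration of study medication or "within 35 days of the last dose of active study medication, the pregnancy should be reported immediately". For men, "any pregnancies in the partner of a male subject during the study or for 35 days after the last dose should also be recorded", once the partner has authorized it. Reported pregnancies are then followed to their outcome. Section 9.1.9 requires contraception "throughout the duration of the study, and for 35 days after last dose of study medication".

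Appendix A places the urine pregnancy test at Screening, at Check-in and at Study Exit or Early Termination. The follow-up column has no test. On the exit date, Section 9.3.4 says "Final Visit procedures will be performed on Day 4 of Period 4".

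One contact follows exit. Section 6.1 says "Follow-up call will be made 14 days ±2 days following the last dose of study drug", and Sections 2.0 and 9.3.5 agree. Appendix A note (d) instead counts the same 14 ± 2 days from study exit. Section 9.3.5 gives the purpose of the call: "to inquire for any ongoing AEs or SAEs, new AEs or SAEs, and concomitant medications taken since final dose of study medication". Note (d) lists the same topics. Note (m) adds: "The routine collection of AEs will continue through to the follow-up phone call". The SAP repeats this schedule in its own Appendix A and adds no later contact.

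**The concern.** A post-dose window for pregnancies is useful only if something in the plan looks for them during it. Here the reporting window and the contact schedule appear to have been set separately. The window runs to 35 days. The last test comes at 3 days, and the last contact comes at about two weeks with pregnancy not among its topics.

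The gap is widest for men. A partner's pregnancy is not a medical occurrence in the subject, so a general question about how he has been feeling (Section 10.2.1.2) would not be expected to bring it out. No scheduled procedure asks him.

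What is at stake is the completeness of safety data. Follow-up to outcome starts only once a pregnancy has been reported. If none is volunteered, a record of no pregnancies would mean only that nobody raised one.

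**Working it through.** **Inputs**
- Four doses 7 days apart (Protocol 6.1): last dose on study day 1 + 3 × 7 = 22.
- Study Exit on Day 4 of Period 4 (9.3.4): study day 25, which is 25 − 22 = 3 days after the last dose.
- Pregnancy window (9.1.10): 35 days after the last dose.
- Follow-up call: 14 ± 2 days from the last dose (2.0, 6.1, 9.3.5), or 14 ± 2 days from study exit (Appendix A note d).
- Screening from Day −28: 28 days before Day 1.

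**Step 1: the plan's own duration.** Section 2.0 gives a total of about 66 days.
- Call counted from the last dose: 28 + 22 + 14 = 64 (range 62 to 66).
- Call counted from study exit: 28 + 25 + 14 = 67 (range 65 to 69).

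Both nominal totals lie within 2 days of 66. The stated duration is reproduced, but it does not show which anchor was meant.

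**Step 2: days after the last test.** 35 − 3 = 32 days, and 32/35 = 91.4%. As the call does not list pregnancy, this is also the share with no planned pregnancy question.

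**Step 3: days after the last contact of any kind.** Days left = 35 − (days from last dose to call).

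| Anchor | Call, days after last dose | Days left of 35 | Share |
|---|---|---|---|
| Last dose | 12 / 14 / 16 | 23 / 21 / 19 | 65.7% / 60.0% / 54.3% |
| Study exit | 15 / 17 / 19 | 20 / 18 / 16 | 57.1% / 51.4% / 45.7% |

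**Step 4: other routes.** Section 10.2.1.1 ends adverse event collection 14 ± 2 days after Study Exit or the last dose. Appendix A note (d) accepts spontaneous adverse event reports to 30 days postdose. That route is passive, is not framed around pregnancy, and stops 35 − 30 = 5 days before the window ends.

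The counts in steps 2 and 3 run from the last dose, so they do not change if washouts exceed 7 days, as Appendix A note (a) allows. They apply to subjects who complete Period 4. After early termination the interval depends on the date of that visit.

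**The case against.** The strongest reply is that Section 9.1.10 is conditional. It says what should happen if a pregnancy occurs and can be read as a duty that begins when the site learns of one. On that reading a reporting window may properly outlast the visit schedule, as spontaneous event reporting already does. This stands as a limit. A reader might infer that the protocol promises active surveillance to day 35 and then breaks the promise, but the text does not go that far. The Section 1.3 amendment summary does speak of pregnancy monitoring time, but about exclusion 11 and the consent elements. The conditional reading still leaves discovery to unsolicited reports.

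Other points on that side also hold:
- Risk is already limited by required contraception, exclusions 11 and 12, and a negative test at each check-in. Section 9.1.9 considers reproductive toxicity unlikely.
- The consent form is not available for review, so subjects may be told there to report a later pregnancy. The call topics are a list, not a script.
- Exclusion 11 also uses 35 days, which might suggest a single window throughout. It counts from participation in the study, not from the last dose, and it screens intention at entry.
- One might argue that the exit test would miss a recent conception. Neither document gives a figure for how early the test detects pregnancy, so nothing here rests on that.
- One might say that most of the window has no contact. That is true at both nominal call times (60% and 51%), but the share falls to 46% at the latest call that Appendix A allows.

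**Conclusion.** The point holds as a gap between a stated window and the means of finding events in it. For a subject who completes the study, 32 of 35 days (91%) have no planned pregnancy test or question. No contact of any kind is scheduled for the last 19 to 23 days under the body-text anchor, or 16 to 20 days under the Appendix A anchor. The two anchors differ by 3 days and contradict each other whatever view is taken of the pregnancy window.

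The conclusion assumes that the topics listed in Section 9.3.5 and note (d) are the planned content of the call. It is a matter of safety data capture only. A reader might extend it to the trial's main result, but the primary endpoints are plasma parameters complete by 72 hours after each dose. The bioequivalence comparison and the sample size are untouched, and the SAP specifies no pregnancy endpoint or table.

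**What to change.** Three changes:

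1. Add a pregnancy question to the follow-up call in Section 9.3.5 and Appendix A note (d). It should cover the subject and, for male subjects, the partner. Record a positive answer on the pregnancy form, with the partner authorization that Section 9.1.10 already requires.
2. State one anchor for the call, the same in Sections 2.0, 6.1 and 9.3.5, in Appendix A, and in the matching SAP text.
3. Reconcile Section 9.1.10 with Section 9.3.5 and Appendix A so that the stated window and the means of finding pregnancies in it agree. If later capture is meant to rely on unsolicited reports, the protocol should say so.

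The length of the window and the means are for the sponsor to decide. The added question alone would cut the unasked part from 32 days to 19 to 23, or 16 to 20 under the Appendix A anchor. A scheduled contact at the end of the present window is not prescribed here. It would take the total to 28 + 22 + 35 = 85 days against about 66, roughly 3 weeks more for each subject reached, and that trade-off is open to argument.

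The cost is one question in a call already planned for up to 72 subjects, plus protocol and eCRF wording. It adds no visit, sample or analysis.
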